This visit will occur five to seven days after Day 3. All participants will complete the Spider Phobia Questionnaire (SPQ; Klorman et al, 1974) and Fear of Spiders Questionnaire (FSQ; Szymanski & O'Donohue, 1995), uploaded in Section 10.1, Item 1.0, to test for change in arachnophobia fear/avoidance symptoms as a function of TMS treatment received. Next, all participants will complete an identical BAT to that completed at their first visit with the same tarantula (see DAY 1 above). Self-report and physiological (i.e., SCR) data will again be collected. After completion of these forms, participants will be debriefed by an un-blinded member of the study team and informed to which group they are assigned. They will be

encouraged to discuss whatever questions or concerns they have regarding the study at that time.

After completion of Day 4, participants will be compensated for their time with one credit per hour of study participation.

Dependent variables (DVs) will be quantitative self-reports and behavioral symptoms of fear and avoidance of spiders both pre- and post-treatment, including SCR (difference between baseline and average level during BAT anticipation period, and number of peaks during BAT), total number of steps completed during the BAT, self-reported distress, anticipatory distress, and maximum distress per BAT step, and total score on the SPQ. BAT measures will be collected for each step and therefore minima, maxima, and means will be compared between the two groups. Primary outcomes examined will be number of steps completed during BAT, self-reported distress during BAT, number of SCR peaks during BAT, SPQ score, and FOS score. All other variables examined will be secondary outcomes. Additionally, for feasibility and tolerability assessment, attendance to TMS treatment sessions and early termination of TMS treatment sessions will be recorded. The primary independent variable examined will be the treatment group (iTBS vs. control iTBS). The sample size will be 40 participants (20 per group). Pre-comparison ANOVA will be performed to limit type 1 error due to multiplicity of comparisons.

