Hypotheses will be tested using between-group two-tailed t-tests given that we are testing not only for magnitude of an effect, but also direction of an effect. We expect that comparisons of efficacy will demonstrate increased confidence during BAT approach, decreased endorsed fear of spiders as measured by SPQ and FSQ, and reduced physiologic response to stimulus (reduced HRV and SCR) with active iTBS and exposure when compared to control iTBS and exposure. We expect that comparisons of feasibility and tolerability will show no significant difference between attendance to, early termination of, or subjective tolerability ratings of TMS treatment sessions between treatment groups.

NOTE 2/2/21: the above reported statistical analysis plan was modified given the small sample size, technical limitations, and distributions of the data observed. The number of statistical tests performed was minimized and multi-level mixed-effects models (MLMs) and nonparametric tests were utilized as appropriate based on the sample size of the experiment. Behavioral measures acquired during the BATs (anticipatory distress, maximum distress, mean skin conductance at each step) were examined using MLMs in Stata version 16.1 as functions of BAT step, group assignment, and timepoint (pre or post-treatment). All other analyses were performed in SPSS (version 26.0.0.0). Demographics and experimental parameters were analyzed for between-group differences using 2-sided Mann-Whitney U Tests. Changes in self-reported fear of spiders (SPQ and FOS) were analyzed using a repeated-measures MANOVA (Greenhouse Geisser correction was applied in case of non-sphericity). A pair of chi-square analyses were performed to validate blinding of the study (based on questionnaires completed by subjects and raters), and no significant deviation from 50/50 chance was observed. A p-value of <0.05 was considered significant for all testing.

ADVERSE EVENT MANAGEMENT

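### The joint repeated-measures MANOVA of SPQ and FOS would by default use only participants with both scales at both visits, and no missing-data rule or analysis set is stated for these two primary outcomes

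*Combined protocol and SAP*

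**What the plan says.** The DAY 4 section lists five primary outcomes: steps completed on the behavioral approach test (BAT), self-reported distress during it, "number of SCR peaks during BAT, SPQ score, and FOS score". I take FOS to be the Fear of Spiders Questionnaire, abbreviated FSQ elsewhere. Of the sample size it says "The sample size will be 40 participants (20 per group"), without an effect size, power or allowance for dropout.

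The NOTE 2/2/21 replaces the planned t-tests. For the two questionnaires it states: "Changes in self-reported fear of spiders (SPQ and FOS) were analyzed using a repeated-measures MANOVA (Greenhouse Geisser correction was applied in case of non-sphericity"). Of the software it says "All other analyses were performed in SPSS (version 26.0.0.0"), and it names no imputation step. Three step-level BAT measures (mean skin conductance, anticipatory distress and maximum distress) are handled differently: they "were examined using MLMs in Stata version 16.1 as functions of BAT step, group assignment, and timepoint (pre or post-treatment").

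On attendance, the OVERVIEW enrols only people able to make all four visits, yet it also provides partial course credit for those who miss visits. Attendance at TMS sessions is recorded as a feasibility measure. No section defines an analysis population, a missing-data rule or the number analysed.

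**The concern.** A MANOVA works on complete response vectors. With two scales at two visits the vector has four entries, and one empty entry removes the person. Two consequences follow. Someone who misses Day 4 contributes nothing, although the Day 1 scores are in hand. Someone with both SPQ scores but one missing FOS form is lost from the SPQ comparison too.

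The mixed models in the same note do not have this restriction, so the outcomes of one trial could rest on different participants without the reader being told. At stake are precision in a trial of 40 and, if loss is related to fear and differs between arms, bias in the group difference for two primary outcomes.

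**Working it through.** **What can be reproduced.** The planned 40 cannot be re-derived, because no effect size, SD or power is given. As a reference point, 20 per arm with a two-sided test at 0.05 has 80% power for d = (1.960 + 0.842) × √(2/20) = 0.886 by the normal approximation, or 0.909 by the noncentral t. This is for a two-group comparison of one mean and stands in for the group effect on one scale.

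**Numbers retained.** Let q be the proportion lost at Day 4 and m the proportion of forms missing independently of each other. Both are assumptions.

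- Joint analysis of four forms: 40 × (1 − q) × (1 − m)⁴
- One scale alone, complete cases: 40 × (1 − q) × (1 − m)²

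| Day 4 loss q | Retained, m = 0 | Joint, m = 5% | One scale, m = 5% | Power at d = 0.909, m = 0 | d for 80% power, m = 0 |
|---|---|---|---|---|---|
| 0% | 40 | 32.6 | 36.1 | 80% | 0.909 |
| 10% | 36 | 29.3 | 32.5 | 75.5% | 0.961 |
| 20% | 32 | 26.1 | 28.9 | 70.1% | 1.024 |
| 30% | 28 | 22.8 | 25.3 | 63.9% | 1.100 |

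The m = 5% columns are on the high side for loss. Eligibility requires a baseline SPQ score, so that form should be complete. With only three forms at risk and q = 0, the joint set is 40 × 0.95³ = 34.3, while SPQ alone would keep 40 × 0.95 = 38.0.

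**Bias, mild scenarios.** Simulation with 200,000 per arm, no true effect, Day 1 to Day 4 correlation 0.5, and probability of loss rising with Day 1 fear (logistic slope 1 per SD):

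| Loss in the two arms | Completer difference in change (SD) | All-available-data likelihood (SD) |
|---|---|---|
| 10% and 10% | −0.004 | −0.004 |
| 20% and 20% | 0.005 | 0.005 |
| 20% and 10% | 0.044 | 0.003 |
| 20% and 0% | 0.085 | −0.001 |
| 30% and 10% | 0.084 | 0.001 |

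The equal-loss rows are zero within simulation error.

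**Bias, severe scenario.** Suppose the most fearful fraction p at Day 1 leaves one arm and nobody leaves the other. The retained Day 1 mean in that arm is −φ(z)/(1 − p), where z is the upper-p normal quantile. Expected change given Day 1 is −(1 − r) times the Day 1 value, so the bias is (1 − r) × φ(z)/(1 − p). At r = 0.6:

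- p = 10%: 0.4 × 0.1755/0.9 = 0.078 SD
- p = 20%: 0.4 × 0.2800/0.8 = 0.140 SD
- p = 30%: 0.4 × 0.3477/0.7 = 0.199 SD

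Across r = 0.8 to 0.5 and these three values of p, the range is 0.04 to 0.25 SD. The arm that loses its most fearful members appears to improve less.

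**Scale.** The SD of change at r = 0.6 is √(2 × 0.4) = 0.894. With 18 against 20 completers the standard error of the difference is 0.894 × √(1/18 + 1/20) = 0.29; with 14 against 20 it is 0.31. The severe-scenario bias is therefore 0.078/0.29 ≈ 0.3 to 0.199/0.31 ≈ 0.6 of one standard error.

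**The case against.** The strongest reply is that nothing shows the problem occurred. No missing value is reported, and with none the MANOVA uses all 40. The design also protects these scales. Stopping an exposure does not end participation, enrolment requires availability for all four visits, and on Day 4 the questionnaires come before the BAT, so refusing the spider that day does not lose them. All of this stands and limits the size of the point. It does not close it, because missed visits are foreseen and no rule covers them.

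A second reply is that the bias comes from the unadjusted change score rather than from deletion as such. This is correct. When loss depends only on Day 1 fear, a completers-only comparison that adjusts for Day 1 is also unbiased. A mixed model on all available data is one sound remedy, not the only one; it also avoids losing a person's SPQ because of a missing FOS form.

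Third, the contrast with the BAT models is narrow. They do not cover steps completed or skin-conductance peaks, both primary, and a person absent on Day 4 gives them only Day 1 information.

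A reader might infer more than the documents support:

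- **That SPQ and FOS were in fact completer comparisons.** No deletion or loss is reported.
- **That the BAT models kept everyone as randomised.** The phrase "as functions of BAT step, group assignment, and timepoint" lists model factors. It does not define an analysis population, and those data could also have been restricted to completers.
- **That the questionnaires were analysed as treated.** The DAY 4 phrase "to test for change in arachnophobia fear/avoidance symptoms as a function of TMS treatment received" is loose procedural wording. The same section makes treatment group the independent variable, and the stimulation site stays fixed after Day 1.
- **That scalp discomfort shows informative loss.** The protocol says the vertex site generally causes less discomfort, which makes unequal loss conceivable. Discomfort is not Day 1 spider fear, which is what the bias figures assume.
- **That the Greenhouse-Geisser clause matters here.** With two visits it cannot change a result, and it was never a missing-data safeguard.

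**Conclusion.** The point holds as a weakness of the named method. For two of five primary outcomes the analysis would default to participants complete on both scales at both visits, and no analysis set or missing-data rule says otherwise. The default follows from the method and the absence of imputation; the documents do not report that anyone was excluded.

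The consequence depends on losses that the documents do not give. With none, there is no effect. With similar loss in both arms, the cost is precision, for example power of 70.1% rather than 80% at d = 0.909 if 20% are lost. Bias of about 0.04 to 0.09 SD needs loss that depends on Day 1 fear and differs by arm. About 0.2 SD needs the deliberately severe case at r = 0.6. A mixed model removes this bias only if loss depends on observed values; it does not protect against loss driven by unobserved Day 4 fear. The change is worth making because a better method is available at little cost, not because the reported result has been shown to be biased.

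**What to change.** Analyse SPQ and FOS separately. For each, fit a linear mixed model with visit, group and group-by-visit, unstructured covariance, REML and small-sample degrees of freedom (for example Kenward-Roger). Include all randomised participants with any value on that scale, by assigned group. Report the group difference in change with a 95% CI, and state the number analysed per outcome and arm, including for the MANOVA and the BAT models.

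The note is in the past tense and records analyses already done, so its text should stand. Present the new models as a re-analysis or sensitivity analysis beside the MANOVA. If every participant has all four values, say so; the missing-data question is then closed.

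The cost is two extra models on data already collected, in software already used for the BAT measures, plus a short table of numbers analysed. Removing the Greenhouse-Geisser clause from any future description, and writing assigned group in the DAY 4 text, are optional wording changes that affect no result.

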- OCD: Obsessive Compulsive Disorder
- GAD: Generalized Anxiety Disorder
- CBT: Cognitive Behavioral Therapy
- SPQ: Spider Phobia Questionnaire
- FSQ: Fear of Spiders Questionnaire
- BAT: Behavioral Approach Test
- SCR: Skin Conductance Response
- HRV: Heart-rate Variability
- RMT: Resting Motor Threshold
- APB: Abductor Pollicis Brevis
- FDI: First Dorsal Interosseus
- vmPFC: Ventral Medial Prefrontal Cortex
